2.1 Duration of Study

The estimated duration of this clinical study is approximately 2 and a half years. This timeline allows one and a half years for site set up and enrollment, 6 months for data collection, and another 6 months for data cleaning, site closure and final study reports. At the time of the 24 week (6-month) postoperative assessment, an End of Study CRF will be completed for every study Subject who has not been prematurely withdrawn (i.e. End of Study CRF was already completed), and study participation will conclude.

3 Subject Definition

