10.9 Analysis Plan

Standard descriptive summaries for continuous data include the number of observations with data, number of observations with missing data, mean, standard deviation, median, minimum, and maximum values. For categorical data, the count (numerator), denominator and percent will be provided. Percentages will be based on the number of subjects without missing data, unless indicated otherwise.

Datapoints will be reported based on the visit date reported by the investigator. In the case where there are multiple visits reported within the same interval, the latest visit (most proximal to date of surgery) will be used for the preoperative timepoint, and the earliest visit will be used for the 6-week timepoint, and the latest (furthest from date of surgery) for the 24-week timepoint. If data is reported before the preoperative window (before -180 days pre-surgery) or after the close of the 24-week window (after 200 days post-surgery), these data will be removed from analysis and a separate analysis will report on the number of such visits.

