10.9.5 Safety Analyses

All safety analyses will be performed on the Safety Population set.

All Adverse Events (AE) from the start of device placement until subject finishes participation in the study will be summarized with frequencies, number of subjects with at least one AE, and percentages for the following categories: Overall, SAE, death, device and procedure related. AEs will also be summarized by Preferred Term within System Organ Class for overall for all reported AEs as well as for the subset of SAEs.

Re-hospitalizations during the study within 90 days post-op and complications within 90 days post-op will be summarized.

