Sticker sheets were created, one set for up to 30 sites, containing treatment assignments for 120 subjects using a fixed block size of 4 and a treatment allocation ratio of 1:1. On the face of each sticker is a character in the sequence A, B, C,, X, Y, Z, AA, AB, AC,AX, AY, AZ, BA, BB, BC, etc...., BX, BY, BZ, CA, etc...

The stickers should be removed sequentially to reveal the randomization code and treatment group ('Study (Kincise)' or 'Control (Mallet)') for each consecutive consented subject that meets eligibility criteria. Peeled sticker should be placed on the screening log to document that randomization was unbiased. The planned randomization group should then be documented in the applicable source document and on the Randomization eCRF (eCRF RDM) in the database.

The assigned treatment will remain secret to site personnel until subject is found to meet all eligibility criteria; No other blinding is implemented in this study.

4 Interval Windows

The study includes the following periods: Pre-op, Operative, Immediate post-op, 6 Week, 24 Week. Intervals related to each are shown in Table 3, below.

Visit	Minimum Day	Maximum Day	Midpoint Day
Pre-Op	-180	0	
Operative	0	0	0
Immediate post-op	0	Discharge	
6 week	14	60	37
24 week	61	200	130

 Table 3
 Interval Windows for Non-Radiographic Study Visits

Time point specific data collected to satisfy the primary and secondary efficacy-related objectives will be assessed for compliance with these intervals. Only data which can be attributed to the visit intervals in Table 3 will be used in the analysis of primary and secondary endpoints. This visit will be hereafter referred to as the Analysis Visit and the originally recorded visit as the Nominal Visit. If multiple measurements fall into the pre-operative window, or into the 'Immediate post-op' post-operative window, the result collected most proximate to surgery will be utilized. For the '6 week' and '24 week' visits, if multiple measurements fall into the window will be utilized for analysis.

5 Levels of Significance

The level of significance is 95%. Primary endpoint analyses, further described in section 8.7, and secondary endpoint analyses with hypotheses, further described in 8.8, will use 1-sided 95% confidence intervals and associated p-values. Data summaries of secondary endpoints without hypotheses and of exploratory endpoints will use 2-sided 95% confidence intervals and associated p-values.

6 Analysis Sets

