8.8.9 Hip Evaluation Functional Recovery Outcomes

All questions on the hip evaluation functional recovery outcomes will be summarized as categorical data using the Per Protocol Analysis Set in the following fashion: recovery time will be the first week (Week 1 – After Week 12) recovery was achieved; Otherwise, recovery time will be "Still cannot do" or "Not Applicable/I never do this" if subject selected these options at the last visit subject was seen.

8.8.10 Radiographic Outcomes (based upon: AP Hip, AP Pelvis, and Lateral) at week 6, week 24

The following radiographic endpoints will be summarized at week 6 and at week 24: Acetabular cup version – Hip, Acetabular cup version – Pervis, Acetabular cup Inclination, Acetabular cup migration, Acetabular cup radiolucency, Acetabular cup osteolysis, Acetabular cup scerotic lines, Acetabular cup porous coating integrity, Femoral stem position, Femoral stem tilt, Femoral stem subsidence, Femoral stem radiolucency, Femoral stem osteolysis, Femoral stem osteolytic lines, Femoral stem coating integrity, Calcar resorption, Calcar fracture, Heterotopic ossification, Proximal femur, Pelvis vertical alignment, Device/anatomy condition.

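### The day-200 cut discards recalled recovery weeks and narcotic durations whose value does not depend on when the visit took place

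*Protocol*

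**What the plan says.** Protocol 10.9 dates data by visit: "Datapoints will be reported based on the visit date reported by the investigator". On late data it says: "after the close of the 24-week window (after 200 days post-surgery), these data will be removed from analysis". The same sentence adds that "a separate analysis will report on the number of such visits". It does not separate measures that change with time from facts the subject recalls.

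SAP 4 (Interval Windows) opens with a statement of scope: "Time point specific data collected to satisfy the primary and secondary efficacy-related objectives will be assessed for compliance with these intervals". It then restricts: "Only data which can be attributed to the visit intervals in Table 3 will be used in the analysis of primary and secondary endpoints". Table 3 closes the 24-week window at day 200 and is titled for non-radiographic visits. The list of substantive changes in SAP 10 does not mention the late-data rule.

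For functional recovery, SAP 8.8.9 says "recovery time will be the first week (Week 1 – After Week 12) recovery was achieved". Otherwise the subject is 'Still cannot do' or not applicable, if that was the choice at the last visit at which the subject was seen. Under Protocol 7.3 and 7.4 the form is first completed at 6 weeks, and later visits take up only unresolved items. SAP 8.8.8 also summarises a recalled item on how long narcotics were taken after surgery.

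Protocol 10.4 says that collected subject data are used for all endpoints. This sits uneasily with a rule that removes some of them.

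**The concern.** A cut-off makes sense for a score that measures the subject's state on the day, such as Harris Hip, EQ-5D-5L or FJS. It makes little sense for a recalled date. An answer given at day 205 about the week in which a subject returned to work falls into the same categories as one given at day 195, because the scale ends at 'After Week 12' (after day 84).

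The form's design makes the loss matter. Recovery after the 6-week visit can only be recorded at a later visit. If that visit is removed, the only remaining answer on the item is the unresolved one from 6 weeks. A subject known to have recovered may then be reported as not recovered or left out of the table. Either way the recovery summaries are distorted, and information already in the database is not used.

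**Working it through.** **1. The plan's own figure.** The documents give no figure for late visits. The nearest stated figure the rule could touch is the power for cup abduction, about 95% with 200 per group (Protocol 10.8). Inputs from Protocol 10.5.2 and 10.8: success rate p = 0.90 (lower end of the anticipated range), margin 0.10, one-sided alpha 0.05, n per group.

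Power = Φ(0.10 / √(2p(1−p)/n) − 1.645)

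- n = 200: 0.10/√(0.18/200) = 3.333; 3.333 − 1.645 = 1.688; power 95.4%. The stated figure reproduces.
- 5% without a usable film, n = 190: 3.249 − 1.645 = 1.604; power 94.6%.
- 10%, n = 180: power 93.5%. 20%, n = 160: power 90.9%.

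The loss arises only for subjects with no in-window film at either postoperative visit, so the effect on the cup test is likely to be small.

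**2. Where the cut falls.** 24 weeks is day 24 × 7 = 168, so the window closes 200 − 168 = 32 days later. Protocol 2.1 equates the visit with six months ("At the time of the 24 week (6-month) postoperative assessment"). Six months is about day 183, which leaves 200 − 183 = 17 days. A visit booked for six months and held 18 days late is outside.

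**3. One subject, followed through the rules.** An item is unresolved at the 6-week visit. There is no visit from day 61 to day 200. At day 205 the subject names the week of recovery.

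| Reading of the last-visit clause in SAP 8.8.9 | Result |
|---|---|
| Removed visit ignored; last usable answer is from 6 weeks | 'Still cannot do' |
| Day-205 visit is the last visit seen, but its data are removed | Missing, and out of the denominator |
| Same subject seen at day 195 instead | Recovered, in the week named |

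**4. Size.** Share of subjects affected per item = f × q × r. All three inputs are assumptions.

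- f: share whose only visit after 6 weeks is later than day 200; 2% to 20%.
- q: share with the item unresolved at 6 weeks; 10% to 50%.
- r: share of those who have recovered by the late visit; 80% to 100%.

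| f | q | r | Share affected | Per 200 |
|---|---|---|---|---|
| 2% | 10% | 80% | 0.16% | 0.3 |
| 5% | 30% | 100% | 1.5% | 3 |
| 10% | 30% | 100% | 3.0% | 6 |
| 20% | 50% | 100% | 10% | 20 |

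Note that f is not the share of late final visits. A subject with any visit in the 140 days from day 61 to day 200 keeps an answer from it.

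**5. Narcotic duration.** The question is on the postoperative hip evaluation, which is completed at 6 weeks as well as at 24 weeks. A subject who had stopped by 6 weeks already has a usable answer. Only those still using at 6 weeks can lose it.

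**The case against.** The strongest reply is that the rule reaches less far than its wording suggests.

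- **Adverse events.** A reader might infer that an event first reported at a day-205 visit is deleted. The documents do not support this. Protocol 10.9.5 has its own rule, under which all events "until subject finishes participation in the study will be summarized", and SAP 8.9 says the same. Events are asked about at every encounter, scheduled or not (Protocol 8), and go on a separate form with its own deadlines (Protocol 8.5). SAP 4 frames windowing as a matter of time-point-specific efficacy data. What remains is a loose end: Protocol 10.9 states no exemption, and complications and re-hospitalisations are listed as secondary endpoints in 10.5.2 but summarised under safety in 10.9.5.
- **Films.** Migration, subsidence, radiolucency and osteolysis develop over time, so windowing them is defensible. Table 3 does not cover films, and Protocol 6 refers to a separate radiographic protocol that is not available here. Only cup angle against plan is arguably independent of visit date, and only where no earlier usable film exists.
- **Last visit seen.** SAP 8.8.9 does not say last in-window visit, so reversion to 'Still cannot do' is one reading and not a certainty. This stands. The alternative under the removal rule is a missing value, which also loses the recovery week.
- **Consequence.** Functional recovery has no hypothesis. Broaching time and OR time are measured on day 0 and are untouched. Protocol 3.5.6 expects missed follow-up to be uncommon, which points to the lower part of the range.

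**Conclusion.** The point holds for recalled items. As written, Protocol 10.9 and SAP 4 discard the recalled week of functional recovery when it is given after day 200. The affected subject becomes missing or 'Still cannot do', and the documents do not settle which. Narcotic duration is affected in the same way, for a smaller group.

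The size is modest and rests wholly on assumed inputs: about 0.2% to 10% of subjects per item, with 3 per 200 as an illustrative middle case. The endpoint is descriptive, so no planned test depends on it. A reader might go further and infer that everything after day 200 is lost, that harms drop out, or that the comparison between arms is biased. The first two are contradicted by the separate adverse-event rules and the day-0 endpoints. The third would need late visits to differ by arm, and nothing in the documents suggests that they do.

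**What to change.** In Protocol 10.9 and SAP 4, limit the day-200 removal to visit-timed measures: Harris Hip, EQ-5D-5L, FJS, current pain, satisfaction and time-dependent film findings. State that answers given after day 200 are kept for the week of functional recovery and the duration of narcotic use, and that a late film is used for cup angle when no earlier usable film exists. This also removes the doubt over the last-visit clause in SAP 8.8.9 and eases the tension with Protocol 10.4.

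As a clarification only, state that the adverse-event, complication and re-hospitalisation summaries follow Protocol 10.9.5 and SAP 8.9 and are not subject to the day-200 cut.

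The cost is a few sentences, with no new data or visits. The small downside is that recall is slightly longer for the late answers, which can be flagged in the table.

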10.9.1 Subject Accounting and Disposition

A subject accounting table and subject disposition table will present the count of subjects by site and overall for all population sets.

10.9.2 Demographic and Procedure Characteristics

All demographic characteristics, surgical, and immediate post-operative details will be summarized for both the Safety Population and the Per Protocol Population.

10.9.3 Primary Endpoint

The primary endpoint analyses, described in section 10.5.1, will be performed on the Per Protocol Population set. The primary endpoint will be summarized as a continuous endpoint for both treatments. The difference in means $\mu_I - \mu_C$ will also be summarized as a continuous endpoint. Its 1-sided upper 95% confidence limit and the p-value for the test of non-inferiority with a margin of 1.25 based on a 2sample t-test will be produced. If non-inferiority is demonstrated, i.e. the p-value is < 0.05 then the test of superiority will proceed, and its p-value will be produced.

10.9.4 Secondary Endpoints

All secondary endpoint analyses will be performed on the Per Protocol Population.

Skin-to-skin OR time in minutes will be summarized as a continuous endpoint for both treatments. The difference in means $\mu_I - \mu_C$ will also be summarized as a continuous endpoint. Its 1-sided upper 95% confidence limit and the p-value for the test of non-inferiority with a margin of 3.75 based on a 2-sample t-test will be produced if the alternative hypothesis of non-inferiority of the primary endpoint is rejected.

The difference between acetabular cup abduction angle and plan for each subject will be summarized as a continuous endpoint for both treatments. The proportion of subjects with acetabular cup abduction angle within 10% of plan will be summarized as a categorical endpoint for both treatments. The difference in proportions $P_I - P_C$ will also be summarized as a categorical endpoint. Its 1-sided lower 95% confidence limit and the p-value for the test of non-inferiority with a margin of 10% based upon a normal approximation method will be produced if the alternative hypothesis of non-inferiority of skinto-skin OR time is rejected.

The difference between acetabular cup version angle and plan for each subject will be summarized as a continuous endpoint for both treatments. The proportion of subjects with acetabular cup version angle within 10% of plan will be summarized as a categorical endpoint for both treatments. The difference in proportions $P_I - P_C$ will also be summarized as a categorical endpoint. Its 1-sided lower 95% confidence limit and the p-value for the test of non-inferiority with a margin of 10% based upon a normal approximation method will be produced if the alternative hypothesis of non-inferiority of acetabular cup abduction angle within 10% of plan is rejected.

With no prospectively planned hypotheses, the following secondary endpoints will be summarized at all visits with available data for both treatments as continuous variables:

- The Harris Hip Score (HHS) and change from baseline HHS
- Forgotten Joint Score (FJS) and change from 6-week postoperative FJS
- EQ-5D-5L and change from baseline
- Pain (Groin, Thigh, and Buttock)
- Patient Satisfaction
- Radiographic Outcomes (based upon: AP Hip, AP Pelvis, and Lateral)
- Length of hospital stay after index THA

With no prospectively planned hypotheses, the following secondary endpoints will be summarized at all visits with available data for both treatments as categorical variables:

- Post-op time when functional activities can be accomplished (return to work; self-care; etc.)
- Narcotic drug usage throughout the study (patient reported)

10.9.5 Safety Analyses

All safety analyses will be performed on the Safety Population set.

All Adverse Events (AE) from the start of device placement until subject finishes participation in the study will be summarized with frequencies, number of subjects with at least one AE, and percentages for the following categories: Overall, SAE, death, device and procedure related. AEs will also be summarized by Preferred Term within System Organ Class for overall for all reported AEs as well as for the subset of SAEs.

Re-hospitalizations during the study within 90 days post-op and complications within 90 days post-op will be summarized.

10.10 Interim Analysis

There are no planned interim analyses for the purpose of stopping the study early. However, some statistical analyses may be performed for conference presentations or abstracts prior to the primary endpoint being reached.

11 Data Management

Electronic Case Report Forms (eCRFs) entered into an electronic data capture (EDC) system will be used to collect all Subject data once a Subject is enrolled in the study. Study sites will be asked to enter Subject data into the eCRFs via the EDC web-based database portal promptly after each subject is enrolled.

For all Subjects, detailed information related to the primary diagnosis, anesthesia type and time, and surgical exposure (*e.g.,* anterior approach), and other surgical variables will be recorded on the Operative Details eCRF. Product code details for each implant and study article (KINCISE adapters as applicable) used during the procedure must be recorded on the Device Log eCRF.

Data collected during the study for each Subject will be maintained as accurately and completely as possible with entries into an EDC system provided by DePuy Synthes. The personal data recorded on all documents and within the EDC system will be regarded as confidential. The Investigator will be responsible for the timing, completeness and accuracy of the details entered within the EDC system. All data entered in the database must have source documents in the Subject's medical records.

The Investigator should retain copies of all documents pertaining to this study (including source documentation, the informed consent document and any other documents to identify the Subjects) for at least two years after this clinical investigation is completed. In addition, if the Investigator moves/retires, etc., she/he should provide DePuy Synthes with the name and address of the person who will be responsible for the Subjects' study related records.

12 Study Implants

The Pinnacle Hip Solutions[®] (Pinnacle cup) system was first launched in 2000. Multiple configurations are now available (see Table 12-1 below).

Cup Style	Image	Description
100		 POROCOAT[®], DUOFIX[®] or GRIPTION[®] coating Available in sizes 48-66 mm (44 & 46mm available in GRIPTION)
Sector		 Three screw holes for optional adjunct fixation - screw hole pattern allows screw access to the ilium and posterior column POROCOAT, DUOFIX or GRIPTION coating Available in sizes 48-66 mm
300		 Three porous-coated spikes enhance initial fixation - spike length is designed to engage the dome of the acetabulum as the rim of the cup engages the periphery of the acetabulum to enhance directional stability of the cup upon impaction POROCOAT coating Available in sizes 48-66 mm
Multihole	(···	 8 -12 screw holes, depending on cup size, for optional adjunct fixation (for more demanding cases or revisions) GRIPTION coating Available in sizes 48-72 mm
Bantam		 For smaller patients or acetabular dimensions, dysplastic acetabuli (DDH) POROCOAT or GRIPTION coating Sizes 38-46 mm

Table 12-1 Pinnacle Hip System Details

The CORAIL[®] Stem was first implanted in 1986 by the ARTRO Group in France. Combining basic design features, including shape, surface finish and extensive hydroxyapatite coating, with a simple compaction broach-only surgical technique, the CORAIL[®] Stem has demonstrated excellent long-term results.

The Actis[®] medial collared DUOFIX[®] hip stem is manufactured from forged titanium alloy (Ti-6A1-4V) and has a sintered commercially pure titanium bead porous coating (POROCOAT[°]), and a thin layer of plasma-sprayed hydroxyapatite (HA) coating.

Figure 12-1 Corail[®] & Actis Stem

Please refer to **Exhibit B** for the CORAIL and Actis stem product codes that can be used in this study.

13 Deviations and Non-compliance Handling

The investigator must not deviate from this protocol. Protocol deviations will be reported to the IRB as applicable per their requirements.

14 Ethical Principles

This clinical investigation shall be conducted in accordance with applicable local laws and regulations and the ethical principles that have their origin in the most recent version of the Declaration of Helsinki. The most recent version of the Declaration of Helsinki can be found here:

https://www.wma.net/policies-post/wma-declaration-of-helsinki-ethical-principles-for-medicalresearch-involving-human-subjects/.

15 Principal Investigator Responsibilities

An Investigator's responsibilities in conducting clinical investigations of a medical device are described below. Additionally, a signed Statement of Investigator (SOI) form will be in place prior to consent of the first subject into the study.

In conducting this medical device clinical investigation, the Investigator is responsible for:

- 1) Ensuring that a clinical investigation is conducted according to applicable regulations for clinical investigations of medical devices, the signed agreement, and the investigational plan; and,
- Protecting the rights, safety, and welfare of subjects under the investigator's care. An Investigator's responsibilities in conducting clinical investigations of a medical device are described in detail below.

